Short Title:	Switch to BIC/FTC/TAF after Renal Transplant
Clinical Phase:	IV
Principal Investigator:	[name]
Study Description:	Hypothesis: We hypothesize that BIC/F/TAF will be efficacious and safe in the management of HIV+ post renal transplant patients, and will have few adverse reactions and drug-drug interactions with tacrolimus in this population
Sample Size:	N = 20
Study Population:	Virally-suppressed HIV+ adults post-renal transplant
Enrollment Period:	November 2020 to May 2023
Study Design:	Single arm, open-label, switch study, following subjects for 48 weeks with a 6 month follow-up
Study Duration:	November 2020 – December 2024
Participant Duration:	In this single arm, open-label, switch study, we propose to switch virally suppressed HIV+ adults post-renal transplant to BIC/F/TAF and follow the subjects for 48 weeks with a 6 month follow-up (Section 6.1).
Study Agent:	BIC/F/TAF® (BIC/F/TAF)
Primary Objectives:	
 1. To determine the efficacy of BIC/F/TAF in HIV+ patients post renal transplant at 24 weeks and 48 weeks post-switch to BIC/F/TAF. 2. To assess the safety and tolerability of BIC/F/TAF in HIV+ patients post renal transplant at 24 weeks and 48 weeks post-switch to BIC/F/TAF. 3. To assess the pharmacokinetics of BIC/F/TAF in HIV+ patients post renal transplant and its interactions with immunosuppressive agents (Tacrolimus) at 12 weeks post-switch to BIC/F/TAF. 4. To assess renal biomarkers including urine protein/creatinine ratio; urine albumin/creatinine ratio; eGFR; serum BUN, creatinine and phosphorus; tacrolimus levels; retinol 2 binding protein and B2 microglobulin post renal transplant at 24 weeks and 48 weeks post-switch to BIC/F/TAF.
Secondary Objectives:	
 1. To assess the incidence of kidney graft rejection after switching to BIC/F/TAF post renal transplant at 24 weeks and 48 weeks post-switch to BIC/F/TAF. 2. To assess the immunologic activity (CD4 count/percentage) of BIC/F/TAF post renal transplant in conjunction with immunosuppressive agents (tacrolimus) at 24 weeks and 48 weeks post-switch to BIC/F/TAF. 3. To determine patient satisfaction with BIC/F/TAF post renal transplant by utilizing a questionnaire to assess health-related quality of life outcomes at 24 weeks and 48 weeks post-switch to BIC/F/TAF.

Primary Endpoints:

1. Proportion of subjects with plasma HIV-1 RNA <50 copies/ml at week 48.

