1.2.2 Secondary Objectives

1. To assess the incidence of kidney graft rejection after switching to BIC/F/TAF post renal transplant.
2. To assess the immunologic activity (CD4 count/percentage) of BIC/F/TAF post renal transplant in conjunction with immunosuppressive agents (tacrolimus).
3. To determine patient satisfaction with BIC/F/TAF post renal transplant by utilizing a questionnaire to assess health-related quality of life outcomes.

2. Background

At NewYork-Presbyterian Hospital-Weill Cornell Medicine, we have a robust Renal Transplant Program, including renal transplantation in HIV+ patients. The Renal Transplant Program works in close collaboration with the Transplant/Oncology Infectious Diseases Program, including clinical research trials. There have been 42 renal transplants performed in HIV+ patients at our institution in the past 10 years, including two HIV to HIV renal transplants. Thirty-seven patients (excluding HIV to HIV renal transplants) remain alive and are eligible for study consideration. Only four are receiving TAF-containing regimens; the remaining 33 are on various antiretroviral (ARV) regimens including protease inhibitors, cobicistat and ritonavir (started by and maintained by their community HIV primary care physicians), which increase drug-drug interactions with tacrolimus and jeopardize the kidney transplant, as well as increasing pill burden. Therefore, a new single tablet ARV with less

drug-drug interactions is important to this unique population. Data from 4 clinical trials (1-5) show that the single tablet regimen containing BIC/F/TAF (Bictegravir/Emtricitabine/Tenofovir Alafenamide) is safe and efficacious and non-inferior to other standard ARV regimens. No patients had to discontinue the drug due to renal events and no patients developed treatment-emergent resistance. BIC had no impact on severe renal impairment (eGFR_{CRG} 15-29 mL/min), no effect on actual GFR (iohexol clearance) and minimal effect on estimated GFR. There were no discontinuations due to adverse renal events and no proximal renal tubulopathy. TAF is a novel tenofovir prodrug (6,7) with improved renal and bone safety compared to Tenofovir. As reported in JAIDS 2016 (5), switching HIV-positive patients with mild to moderate renal impairment from a prior TDF-based regimen to Elvitegravir/Cobicistat/Emtricitabine/TAF (E/C/F/TAF) resulted in significant decreases in proteinuria, albuminuria and tubular proteinuria without dose adjustment.

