Kidney transplantation is successful in HIV+ patients although rejection rates are higher than in non-HIV+ transplant patients (8). The greatest clinical challenge is to achieve therapeutic and nontoxic levels of the immunosuppressive drugs, especially Tacrolimus, in this population, due to the complicated pharmacokinetic interactions of these agents with antiretroviral agents (ARV), especially protease inhibitors, cobicistat, and ritonavir (8). Non-therapeutic exposure to tacrolimus contributes to higher rate of rejection, so it is important to study ARV agents with less drug-drug interactions that are safe in this special population. We are currently completing a manuscript addressing this issue at our institution and the kidney transplant team has presented preliminary data in a poster at the American Transplant Congress in 2018 (Al Jurdi, Clinical Outcomes of HIV-Infected Kidney Transplant Recipients With An Early Corticosteroid Withdrawal Protocol). It is important to closely follow the CD4 lymphocyte counts and percentages in this unique population and the effect on HIV infection and immunosuppression. Preferred ARV regimens in HIV+ patients post renal transplant include integrase inhibitors and TAF, with the goal to avoid protease inhibitors, ritonavir and cobicistat and decrease drug-drug interactions with tacrolimus (8,9).

In treatment naïve adults with HIV-1 infection, switching from DTG, abacavir, and lamivudine to BIC/F/TAF proved to be a safe and efficacious option for the treatment of HIV-1 infection (1). The pharmacokinetics of BIC/F/TAF were assessed in this study, and the mean trough concentrations of BIC were 14 times higher than the protein-adjusted 95% effective concentration against wild type HIV-1 virus.

There is no current data about the pharmacokinetics of BIC/F/TAF in renal transplant recipients or the interactions of BIC/F/TAF with tacrolimus. Previous work has demonstrated sustained, zero-order, linear, release pharmacokinetic characteristics of TAF (10,11). TAF is metabolized via CES1 in hepatocytes, cathepsin A in PBMCs, and minimally with CYP3A. Tenofovir plasma levels significantly increase when administered to subjects with moderate to severe renal impairment, such that the dosing interval is adjusted in patients with baseline creatinine clearance below 50 mL/min based on modeling of single-dose pharmacokinetic data in non-HIV and non-HBV infected subjects with varying degrees of renal impairment (12).

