3.1 Overall Design

We hypothesize that BIC/F/TAF will be efficacious and safe in the management of HIV+ post renal transplant patients, and will have few adverse reactions and drug-drug interactions with tacrolimus in this population.

Eighteen subjects will be enrolled in this Phase IV, single arm, open-label, single-site, switch study. In this study, virally suppressed HIV+ adults will be switched post-renal transplant from their current anti-retroviral regimen to BIC/F/TAF and will be followed for 48 weeks with a 6 month follow-up (Section 6.1). Informed consent will be obtained before starting the study (Section 6.1).

Patients will have bloodwork completed throughout the study, as shown in the Schedule of Assessments (Section 6.1).

A health-related quality of life questionnaire (Appendix) will be administered to each patient to assess satisfaction with a one pill regimen as well as adverse events (Section 6.1).

Pharmacokinetic (PK) studies will be assessed at Week 12 when the renal function is stable (decided by PI). Intracellular TAF levels by dried blood spot will be collected during the Week 12 visit as well as Week 24, Week 36, Week 48, Month 6 Follow-up. Intracellular TAF levels by PBMC will be collected once during the Week 12 visit. An intensive pharmacokinetic day will take place at the Week 12 visit. This bloodwork is outlined in Section 6.1. Bloodwork for the intracellular TAF level testing and pharmacokinetic testing will be stored and sent to [name] at the University of Colorado's Antiviral Laboratory. (14-16)

Note: Patients switched post-renal transplant from their current anti-retroviral regimen to BIC/F/TAF prior to identification for this study may also be enrolled. This group will be referred to as "Group 2". Pharmacokinetic testing for Group 2 subjects will be completed once each Group 2 subject's tacrolimus levels are stable as per the Principal Investigator for 2-4 weeks. All standard of care lab values and concomitant medications will be collected from Group 2 subjects for 60 days prior to and after the Biktarvy switch date and for the duration of Biktarvy therapy. Any adverse events related to Biktarvy prior to enrollment will be recorded.

Sample Collection

Samples include plasma and peripheral blood mononuclear cells (PBMC). Blood is collected in EDTA tubes for plasma separation. CPT vacutainers are used to isolate PBMC, which are counted with an

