automated countess cytometer (Invitrogen™, Thermo Fisher Scientific Corporation, Carlsbad, CA) and lysed. BIC, F, and TAF in plasma are assayed using a validated LC/MS/MS methodology with a lower limit of quantification (LLOQ) of 10 ng/mL (16).

Determination of Pharmacokinetic Variables

The pharmacokinetic variables for BIC/F/TAF are calculated from the concentration-time data using noncompartmental methods. The peak drug concentration (C_{max}) and time of peak drug concentration are obtained directly from the observed data. The terminal elimination rate constant (k_{el}) is obtained from a log-linear regression of the plasma concentration compared to time data in the terminal post distribution phase. The elimination half-life ($t_{1/2}$) is calculated from $0.693/k_{el}$. The area under the plasma drug concentration-versus-time curve (AUC_{0-24}) and the area under the moment curve from 0 to 24 h ($AUMC_{0-24}$) are calculated by the log-linear trapezoidal rule. The area under the plasma drug concentration-versus-time curve from time zero to time infinity ($AUC_{0-\infty}$) is obtained from the following equation: $AUC_{0-24} \cdot C_t/k_{el}$, where C_t is the last measurable concentration and k_{el} is the terminal elimination rate constant. The total body clearance (CL) is obtained from the equations $dose/AUC_{0-\infty}$ and $dose/AUC_{0-24}$ (presumed steady state, where 24 h is the dosing interval), respectively. The volume of distribution (V_d) is calculated as follows: $V_d = CL/k_{el}$. The steady-state volume of distribution (V_{ss}) is calculated from the product of CL and the mean residence time. The mean residence time is obtained from the following equation: $(AUMC_{0-\infty}/AUC_{0-\infty}) T/2$, where $AUMC_{0-\infty}$ is extrapolated from $[(C_t \times t)/k_{el} \times C_t/k_{el}]$ and where T is the infusion time, all other terms having been previously defined.

Statistical Analyses and Sample Size

This is a pilot study of the efficacy, safety, and pharmacokinetics of BIC/F/TAF in HIV+ renal transplant recipients. Sample size is based upon feasibility of enrolling the current cohort of patients on the WCM/NYPH renal transplant service who are currently receiving antiretroviral therapy. Among the 37 HIV+ renal transplant recipients who are followed at NYPH and who are currently eligible for the study, we project that 20 patients will enroll into this study and complete treatment.

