We hypothesize that in the transition from a standard antiretroviral regimen to a BIC/F/TAF regimen, there would be high probability of a sustained suppression of HIV- RNA (1). In the randomized, double-blind, multicenter, active-controlled, phase 3, non-inferiority clinical trial of switching to fixed-dose bictegravir, emtricitabine, and tenofovir alafenamide from dolutegravir plus abacavir and lamivudine in virologically suppressed adults with HIV-1 by Molina et al, the primary endpoint was the proportion of participants with plasma HIV-1 RNA of 50 copies per mL or higher at week 48 that fulfilled the prespecified non-inferiority margin of 4%, where three (1%) of 282 in the bictegravir group had HIV-1 RNA of 50 copies per mL or higher at week 48 versus one (<1%) of 281 participants in the dolutegravir group (difference 0.7%, 95.002% CI -1.0 to 2.8; $p=0.62$).

The number of 20 subjects who are projected for enrollment and study completion will provide sufficiently robust data for pharmacokinetic studies to yield a coefficient of variation of <15%, which will permit a robust analysis and model development.

Outcome variables and adverse events will be reported using descriptive statistics, including means, medians, ranges, and standard errors.

The relationship between renal function, tacrolimus levels, BIC/F/TAF plasma concentrations, and intracellular concentrations of TAF will be determined by linear regression analysis.

4. Subject Selection

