10.1 Study Design/Endpoints

We hypothesize that in the transition from a standard antiretroviral regimen to a BIC/F/TAF regimen, there would be high probability of a sustained suppression of HIV- RNA (1). In the randomized, double-blind, multicenter, active-controlled, phase 3, non-inferiority clinical trial of switching to fixed-dose bicitegravir, emtricitabine, and tenofovir alafenamide from dolutegravir plus abacavir and lamivudine in virologically suppressed adults with HIV-1 by Molina et al, the primary endpoint was the proportion of participants with plasma HIV-1 RNA of 50 copies per mL or higher at week 48 fulfilled the prespecified non-inferiority margin of 4%, where three (1%) of 282 in the bicitegravir group had HIV-1 RNA of 50 copies per mL or higher at week 48 versus one (<1%) of 281 participants in the dolutegravir group (difference 0.7%, 95.002% CI-1.0 to 2.8; p=0.62).

The number of 20 subjects who are projected for enrollment will provide sufficiently robust data for pharmacokinetic studies to yield a coefficient of variation of <15%, which will permit a robust analysis and model development. Outcome variables and adverse events will be reported using descriptive statistics, including means, medians, ranges, and standard errors. The relationship between renal function, tacrolimus levels, BIC/F/TAF plasma concentrations, and intracellular concentrations of TAF will be determined by linear regression analysis.

Expected Outcomes:

1. We expect sustained suppression of the HIV viral load throughout the study.
2. We expect that BIC/F/TAF will be well tolerated in the HIV+ renal transplant population with minimal adverse events and preservation of renal function with stable tacrolimus levels.
3. Plasma concentrations of BIC/F/TAF will follow those reported in HIV+ non-renal transplant recipients and drug/drug interactions with tacrolimus will be minimal, allowing easy adjustment with minimal detrimental effects on renal function.

11. Adverse Events

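### Tacrolimus results are not separated by prior booster or protease inhibitor use, so a change across the switch cannot be attributed to BIC/F/TAF

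*Combined protocol and SAP*

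**What the plan says.** The synopsis describes the design as "Single arm, open-label, switch study, following subjects for 48 weeks with a 6 month follow-up". Primary objective 3 (synopsis and Section 1.2.1) covers the pharmacokinetics of BIC/F/TAF and its interaction with tacrolimus; the synopsis sets it at 12 weeks after the switch. The third expected outcome in Section 10.1 is that "drug/drug interactions with tacrolimus will be minimal, allowing easy adjustment with minimal detrimental effects on renal function".

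Section 2 (Background) describes the 37 candidate patients: "Only four are receiving TAF-containing regimens; the remaining 33 are on various antiretroviral (ARV) regimens including protease inhibitors, cobicistat and ritonavir". It explains that therapeutic, nontoxic tacrolimus levels are hard to achieve "due to the complicated pharmacokinetic interactions of these agents with antiretroviral agents (ARV), especially protease inhibitors, cobicistat, and ritonavir". Sections 4.2 and 4.3 place no limit on the prior regimen, except that BIC/F/TAF must not be the only antiretroviral therapy ever used. Boosted and unboosted patients can both enter.

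The analysis, given in Section 3.1 and repeated in Section 10.1, has two parts. Outcomes are summarised descriptively, and "The relationship between renal function, tacrolimus levels, BIC/F/TAF plasma concentrations, and intracellular concentrations of TAF will be determined by linear regression analysis". Neither part mentions the prior regimen.

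**The concern.** The objective and the expected outcome concern a property of BIC/F/TAF. In a patient coming from a boosted regimen, two things change together: a drug known to interact with tacrolimus is withdrawn, and BIC/F/TAF is started. With no control arm, nothing in the all-subject data separates the two.

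The error can run either way. If level-per-dose is summarised, booster withdrawal appears as a change and may be reported as a BIC/F/TAF interaction. If raw levels are summarised after the tacrolimus dose has been adjusted, levels can look stable, and a minimal interaction may be reported from patients who carry no separate information on BIC/F/TAF. Section 2 states that no data exist on this interaction, so a misattributed result would have nothing to correct it.

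**Working it through.** **The plan's own figure.** There is no power calculation to reproduce. The sample size is a feasibility projection: 20 of 37, or 20/37 = 54%. (The overall-design text in Section 3.1 says eighteen, or 18/37 = 49%. The two should be reconciled, but the point here does not depend on which is right.)

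**What the documents give on the mix.** Four of the 37 take TAF-containing regimens and 33 take others. If all 20 subjects come from the 37, at least 20 − 4 = 16 come from the 33. How many of those are boosted is not stated. The four TAF-containing regimens are not necessarily unboosted, because Section 2 itself describes a TAF combination that contains cobicistat.

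**Is the prior regimen used anywhere?** It is absent from the descriptive analysis, from the regression and from the eligibility criteria (apart from the one exclusion noted). Pooling therefore arises by omission; no sentence prescribes it.

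**Are the data for a before/after reading collected?** Yes. The Schedule of Assessments has tacrolimus levels on Day 1 and at later visits, and Group 2 contributes standard-of-care laboratory values from 60 days before the switch. Tacrolimus dose is not a scheduled item. Pre-switch concomitant medications are specified only for Group 2.

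**Illustration of size.** These inputs are assumptions, since the documents give none of them: R, the factor by which a booster raises tacrolimus level-per-dose; f, the share of subjects boosted before the switch; and a true BIC/F/TAF effect of 1.00. On the log scale a boosted subject changes by −ln R and an unboosted subject by 0. The mean is −f·ln R, so

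pooled post/pre geometric mean ratio = R^(−f).

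| R | f = 25% | f = 50% | f = 75% |
|---|---|---|---|
| 1.5 | 0.90 | 0.82 | 0.74 |
| 2 | 0.84 | 0.71 | 0.59 |
| 3 | 0.76 | 0.58 | 0.44 |

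For example, 2^(−0.5) = 0.71. The ratio equals 1.00 only if f = 0 or R = 1, and R = 1 would contradict Section 2.

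**Would it show at N = 20?** Assume a within-patient CV of 30%. The log-scale SD of a paired change is √2·√ln(1 + 0.3²) = 0.415. The mixture adds f(1 − f)(ln R)² to the variance. The 90% half-width is 1.729·SD/√20.

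- f = 50%: 0.68–0.98 (R = 1.5), 0.57–0.87 (R = 2), 0.44–0.75 (R = 3). All exclude 1.00.
- f = 25%: 0.76–1.08 (R = 1.5), 0.69–1.03 (R = 2). Both include 1.00.

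**After separating the groups.** With no BIC/F/TAF effect, the unboosted group is centred on 1.00 and the boosted group on 1/R. At the same assumed CV, the expected 90% interval for the unboosted group is 0.79–1.27 with 10 subjects and 0.67–1.49 with 5.

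**The case against.** The strongest reply is that the plan defines no before/after tacrolimus ratio and no level-per-dose measure. The one named tacrolimus analysis is a regression on drug concentrations. BIC/F/TAF plasma concentrations are scheduled only at Week 12 and intracellular TAF from Week 12 onward, after the booster has stopped. This stands. The table above measures bias in a summary that the plan does not spell out, and it should be read as hypothetical. It does not remove the problem: the objective needs some contrast to be answered, tacrolimus is measured before and after the switch, and the expectation of stable levels in Section 10.1 invites that comparison.

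A second reply is that the net effect of leaving a boosted regimen is a legitimate descriptive target in a feasibility-sized pilot, and that the expected outcome already allows for adjustment. This also stands, provided the result is worded as a net switch effect and not as a property of BIC/F/TAF.

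A third is that the unboosted group may be very small. That is true and limits precision. It does not make the all-subject figure an estimate of the right quantity.

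A reader might go further and infer that the correlation of rejection with tacrolimus levels (secondary endpoint 2) fails for the same reason, or that every regression involving tacrolimus needs a booster term. The documents do not support either. That correlation is not defined as a change across the switch, and the regression uses concentrations measured after it. An extra term would also cost a parameter at this sample size.

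**Conclusion.** The point holds. The protocol names the interacting drugs, admits patients who take them, has no control arm and never uses the prior regimen in the analysis. An all-subject summary of tacrolimus change across the switch cannot answer primary objective 3 as a statement about BIC/F/TAF.

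This conclusion rests on the documents alone; its size does not. Under the assumed R of 1.5 to 3 and f of 25% to 75%, the pooled ratio runs from 0.90 down to 0.44 when the true effect is 1.00. A reader might infer that most of any observed change is booster withdrawal, or that a false interaction is bound to be reported. Neither follows, because R, f and the within-patient variation are not given, and at the mild end of the range the pooled interval still includes 1.00.

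**What to change.** In Sections 3.1 and 10.1, with matching data items in Section 6.1:

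- For all subjects, record the antiretroviral regimen taken immediately before the switch and the tacrolimus dose in use at each tacrolimus level.
- Describe tacrolimus level, dose and level-per-dose, pre-switch versus post-switch, separately for subjects with and without a prior booster (ritonavir or cobicistat) or protease inhibitor.
- For prospectively switched subjects, use Day 1 to Week 12. For Group 2, use pre-switch records to the pharmacokinetic visit held once tacrolimus levels are stable, and show these subjects separately, because they enter the schedule at the investigator's discretion and have no common Day 1 baseline.
- Base any statement about a BIC/F/TAF–tacrolimus interaction on the unboosted subjects, with an interval. If too few are unboosted, state that the interaction could not be isolated.
- Describe the boosted subjects' change as the net effect of the regimen switch.

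The cost is two recorded fields and a smaller, less precise group behind the interaction statement. No visit, sample or subject is added, and tacrolimus management is unaffected.
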